## **AIMS**

ICD-11 CPTSD is a new condition and there are currently no identified effective treatments to enable recovery from this debilitating condition. Identifying effective interventions to treat veterans with CPTSD is therefore of paramount importance. We have recently proposed in the research literature a new innovative person-centred treatment approach for CPTSD (i.e. modular therapy; Karatzias and Cloitre, 2020). Enhanced Skills Training in Affective and Interpersonal Regulation (ESTAIR) involves targeting the symptoms of CPTSD clusters sequentially using concrete modules (i.e. specific number of sessions targeting specific clusters of symptoms). This intervention has never been tested in a military population before.

The project will provide information on recruitment and acceptability of a new treatment for CPTSD. The following main research questions will be addressed as part of this pilot project:

- I. Is it feasible to recruit for a study on ESTAIR vs. TAU in military personnel during the study recruitment period?
- II. What is the retention rate in the study at the end of treatment and at 3-month follow-up?
- III. Are primary and secondary outcomes acceptable from participants?
- IV. Is the new ESTAIR protocol acceptable by people with CPTSD?

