3. Given the decision to offer modules sequentially (see point 1 above), session 25 (summary and relapse-prevention) was modified. In order to avoid repetition of the content of final session of the PTSD module (that summarizes the client's work in relation to PTSD symptoms) and session 25 (that summarizes the client's work across all ESTAIR modules), it was decided that for the purposes of the present pilot it would be more suitable to extend the time allotted for the final PTSD module session to incorporate additional content of session 25.

Defined completers will be those who have a valid post-treatment assessment using the ITQ at the end of every module and are diagnosis free. The ITQ will be administered at the end of every module and if the person is CPTSD diagnosis free then they will be offered a full post-treatment assessment. Subsequent input from Combat Stress following completion of trial will be offered as required and as per normal service standards.

**Update Note:** The ITQ will be administered at the end of every module to inform clinician's understanding of veteran difficulties. Participants will receive all four treatment modules, and dropping below CPTSD diagnosis on the ITQ at the end of a module will not serve as an indication to end treatment. Treatment will run include all four modules, unless strong clinical rationale to not do so.

**Update Note:** Treatment "defined completers" will be those who complete 80% of treatment sessions and have received at least 1 session per module. This definition was added ad-hoc, as it was noted that the protocol was lacking a "defined completer" definition and concerns were raised that the absence of such a definition would risk overattributing drop-outs/withdrawals to the treatment and would limit the opportunity to attribute such drop-outs to non-treatment related factors.

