### **Somatic Symptoms**

Medically unexplained symptoms will be assessed using the *Patient health Questionnaire-15* (PHQ-15; Kroenke et al., 2002). The scale includes the most prevalent DSM-IV somatization disorder somatic symptoms. Participants are required to rate the severity of 13 symptoms as 0 (“not bothered at all”), 1 (“bothered a little”), or 2 (“bothered a lot”). Responses are coded as 0 (“not at all”), 1 (“several days”), or 2 (“more than half the days” or “nearly every day”) to produce total scores ranging from 0 to 30 and scores of  $\geq 5$ ,  $\geq 10$ ,  $\geq 15$  represent mild, moderate and severe levels of somatization. The reliability and validity of the PHQ-15 are acceptable.

**Update Note: Friends and Family Test (FFT).** The FFT was added as an additional secondary measure to help infer the acceptability of the ESTAIR intervention in comparison to TAU. The FFT is a single item asking participants to indicate ‘how likely is it that you would recommend our service to your GP, family and friends if they needed similar care?’. Responses are indicated on a 5 point-Likert scale ranging from 1 (‘Extremely unlikely’) to 5 (‘Extremely likely’). The FFT is standardly administered as an end-of-treatment measure at Combat Stress.

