## **Qualitative outcomes**

Qualitative data will be collected to explore the acceptability of the ESTAIR intervention. It was initially intended to invite a total of 4 completers and 4 non-completers from the ESTAIR arm to participate in a one-off qualitative interview. In order to enhance understanding of the acceptability of ESTAIR and to manage feasibility concerns, it was decided that all participants in the ESTAIR arm would be asked to answer specific, brief questions assessing their experience of the protocol, their perception of treatment in general, and suggestions for improvement.

**Update Note:** Given concerns that the specific questions administered to all participants completing the ESTAIR intervention would not provide rich enough data to infer the acceptability of the ESTAIR protocol, two safeguards are put in place for collecting qualitative data. Prior to completing the self-report qualitative questions, the research assistant will call participants to explain purpose of the qualitative items and will explain that responses will be anonymised by participant number and that they will not be shared with the therapist. If at the end of collection of qualitative data, responses do not appear rich enough to answer research questions 3 and 4, efforts will be made to recruit an independent research assistant/assistant psychologist to administer the one-off interviews to 4 completers and 4 non-completers from the ESTAIR arm. This will be done by an independent research assistant/assistant psychologist to reduce biases in interview responses, should they be required.

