## **PROCEDURE**

Potential participants will be screened by the MDT team, and eligible participants will be contacted by the research assistant. As previously described in the **Recruitment** section above, eligible participants will be provided with the patient information sheet and consent form. Potential participants will be contacted by the research assistant, who will ensure that they have received an information sheet and will answer any questions. All potential participants will be reminded that participation is entirely voluntary and that deciding not to

take part in the study will have no impact upon the clinical care they receive. They will also be informed of their right to withdraw from the study at any time, without giving a reason, and reassured that exercising their right to withdraw will have no impact upon the ongoing care they receive. Potential participants who wish to take part will need to provide informed consent. Participants who are not eligible or who do not want to participate will be offered routine care as per Combat Stress procedures.

Eligible participants who provide consent to take part will complete baseline measures and will then be randomized to either the ESTAIR or TAU intervention arm. At 25-weeks (post-treatment), participants will be contacted by the research assistant to complete post-intervention measures. Participants in the ESTAIR arm will also be asked to provide qualitative data of their experience of intervention. The research assistant will then set an appointment to again contact participants in 12-weeks' time to complete the follow-up measures.

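### The protocol is inconsistent on whether ESTAIR non-completers are asked the acceptability questions, which puts research question IV at risk of over-favourable answers

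*Combined protocol and SAP*

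**What the plan says.** The fourth research question under Aims is "Is the new ESTAIR protocol acceptable by people with CPTSD". It refers to people with the condition, not to those who finish treatment. Participant views on acceptability are also listed under Outcome Measures.

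The protocol describes the respondents in three places:

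- Qualitative outcomes, first paragraph: "all participants in the ESTAIR arm would be asked to answer specific, brief questions assessing their experience of the protocol".
- Procedure, in the account of the 25-week contact: "Participants in the ESTAIR arm will also be asked to provide qualitative data of their experience of intervention".
- Qualitative outcomes, Update Note: "specific questions administered to all participants completing the ESTAIR intervention".

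The initial intention was to interview four completers and four non-completers. Those interviews are now a fallback. The condition is "If at the end of collection of qualitative data, responses do not appear rich enough to answer research questions 3 and 4", and the commitment is then that "efforts will be made to recruit an independent research assistant/assistant psychologist to administer the one-off interviews to 4 completers and 4 non-completers".

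The FFT was added, in an Update Note under Somatic Symptoms, to help compare the acceptability of ESTAIR with that of TAU. On timing, that note says only: "The FFT is standardly administered as an end-of-treatment measure at Combat Stress". The FFT does not appear in the list of measures under Outcome Measures or in Procedure.

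**The concern.** People who stop a therapy early are a natural place to look for those who found it unacceptable. Read alone, the Update Note would let a research assistant comply with the protocol while asking only those who finished. The interview fallback does not close the gap. Full and thoughtful answers from completers could satisfy a richness test while no drop-out has been heard. The judgement is also made once collection has ended, which may be long after an early drop-out has left.

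The FFT has a related weakness. A measure tied to the end of treatment has no obvious moment for someone who leaves midway. The Update Note on TAU describes that arm as a mental health assessment, so its end of treatment is unclear too.

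At stake is one of the four questions that the pilot was set up to answer.

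**Working it through.** No figure in the plan can be reproduced here. The protocol gives no acceptability rate, target or margin for research question IV, and the sample size is described as pragmatic (2 × 30 = 60). The check is therefore a comparison of the texts, followed by a sensitivity calculation on assumed values.

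**Step 1: who is asked.** Two statements name the ESTAIR arm without a completion condition, and one names those completing. The odd one out is the Update Note, which comments on the paragraph before it. Its stated worry is thin data, and it does not say that it narrows the respondents. However, the Adverse Events section uses nearly the same completion wording for the trial-completer version of its questionnaire and deals with withdrawers separately. The ESTAIR section also has a formal completer definition: "complete 80% of treatment sessions and have received at least 1 session per module". The note can therefore fairly be read as excluding drop-outs. The texts conflict, and nothing says which governs.

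**Step 2: what else reaches drop-outs.**

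- The early-withdrawal adverse events questionnaire covers harms, not acceptability, and is filled in with the therapist. For the acceptability questions, participants are told that the therapist will not see their answers.
- Retention and non-attendance data show that people left, but not why.
- The FFT has no stated time point for drop-outs or for TAU.
- No section says how people who stop treatment are approached for the acceptability questions, or how missing answers are reported.

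**Step 3: how large a completers-only distortion could be.** Let c be the number completing out of 30, and let pC and pN be the proportions of completers and non-completers who find ESTAIR acceptable. None of the three is given in the documents.

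Whole-arm proportion = (c × pC + (30 − c) × pN) / 30

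Overstatement = (1 − c/30) × (pC − pN)

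Take pC = 0.90 (assumed). With c = 23 and pN = 0.60, the whole-arm value is (23 × 0.90 + 7 × 0.60) / 30 = 24.9 / 30 = 0.83, an overstatement of 7 points. Over a range, in percentage points:

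| Completers of 30 | pN = 0.9 | pN = 0.6 | pN = 0.3 | pN = 0 |
|---|---|---|---|---|
| 27 | 0 | 3 | 6 | 9 |
| 23 | 0 | 7 | 14 | 21 |
| 15 | 0 | 15 | 30 | 45 |

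The rows for 23 and 15 are anchored loosely to the progression criterion of 25-week ITQ data from at least 75% of those randomised. With equal retention that is 0.75 × 30 = 22.5 per arm. If all 60 − 45 = 15 permitted losses fell in ESTAIR, 15 would remain. Supplying ITQ data is not the same as completing treatment, so these rows only indicate scale.

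**Step 4: reach of the fallback, if used.** Four interviews would cover 4/7 = 57% of non-completers when 23 complete, and 4/15 = 27% when 15 complete. If it is not triggered, it covers none.

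**The case against.** The strongest reply is that the plan already asks everyone. The decision in Qualitative outcomes is stated for the whole arm, and Procedure repeats it at a fixed contact with no completion condition. The contrary phrase sits in a clause explaining why safeguards were added. This stands. A reader might infer that the protocol has settled on a completers-only design, and the documents do not support that. What remains is an unreconciled conflict, and the note is the wording that staff could reasonably take as current.

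A reader might also infer that the answer to research question IV is biased upward by a stated amount. That is not supported either. The Qualitative analyses section plans a summary and thematic analysis, and the progression criteria contain no acceptability rate. The protocol itself, in explaining its completer definition, allows that drop-out may have causes unrelated to treatment. Non-completers cannot simply be equated with people who disliked ESTAIR.

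On the fallback, the test is whether responses can answer the research questions, and a careful team might judge that missing non-completers fail it. That is possible, but the wording does not require it.

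On the FFT, the end-of-treatment sentence describes service practice, and both arms share a 25-week assessment that could carry the item. That is fair. The gap is that the FFT is not assigned to that assessment. It does not follow that drop-outs or TAU participants will be missed.

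Retention data, adverse events data from withdrawers and clinical staff views all bear on acceptability, but none replaces asking those who left.

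**Conclusion.** The concern holds as an inconsistency with a plausible consequence. Qualitative outcomes contradicts itself, and its Update Note contradicts Procedure, on whether the acceptability questions go to the whole ESTAIR arm or to those completing. If the note is followed, research question IV risks over-favourable answers. Neither the interview fallback nor the FFT, as described, guards against that.

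The size cannot be stated from the documents. It is zero if the two groups agree. With 23 of 30 completing and an assumed 90% of completers favourable, it is 7 to 21 points for assumed gaps of 30 to 90 points. Because the outcome is thematic with no threshold, these figures show scale only, and no planned decision rule turns on them. This is a cheap improvement worth making, not a flaw that undermines the trial.

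**What to change.** 1. Reconcile Qualitative outcomes with Procedure. State that all randomised ESTAIR participants, including those who stopped treatment but still agree to contact, are asked the brief questions at the existing 25-week contact.
2. Assign the FFT to that same contact in both arms, and add it to the list of measures under Outcome Measures.
3. Report answers by completion status, with the number asked, answering and not reached in each group. Name the completer definition used, since the ESTAIR section contains more than one.

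The cost is small, because the research assistant already contacts participants at 25 weeks and the added items are brief. The drawback is that drop-outs will probably respond less often. Reporting the number not reached makes that visible.

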## **PROCEDURE**

Potential participants will be screened by the MDT team, and eligible participants will be contacted by the research assistant. As previously described in the **Recruitment** section above, eligible participants will be provided with the patient information sheet and consent form. Potential participants will be contacted by the research assistant, who will ensure that they have received an information sheet and will answer any questions. All potential participants will be reminded that participation is entirely voluntary and that deciding not to

take part in the study will have no impact upon the clinical care they receive. They will also be informed of their right to withdraw from the study at any time, without giving a reason, and reassured that exercising their right to withdraw will have no impact upon the ongoing care they receive. Potential participants who wish to take part will need to provide informed consent. Participants who are not eligible or who do not want to participate will be offered routine care as per Combat Stress procedures.

Eligible participants who provide consent to take part will complete baseline measures and will then be randomized to either the ESTAIR or TAU intervention arm. At 25-weeks (post-treatment), participants will be contacted by the research assistant to complete post-intervention measures. Participants in the ESTAIR arm will also be asked to provide qualitative data of their experience of intervention. The research assistant will then set an appointment to again contact participants in 12-weeks' time to complete the follow-up measures.

### **Participant Withdrawal or Discontinuation**

Participants are free to withdraw from the study at any point, without giving any reason and without their legal rights or usual care being affected. Investigators may also withdraw participants if they deem their continuation to be harmful. The trial management group will review all instances of adverse events, whether they are judged to be attributable to the trial or interventions, and, based on this information, determine whether the participant should be withdrawn. Non-identifiable data from participants who have been withdrawn will be used to assess the feasibility of the study.

Participant engagement may be discontinued based on adverse events. In the instance of an adverse event, the clinician will inform the trial management group. The trial management group will review this form and determine whether the event could reasonably be attributed to the intervention or participation in the trial. The trial management group will review all instances of adverse events, whether or not they are judged to be attributable to the trial or interventions, and, based on this information, determine whether the participant should be withdrawn and/or whether the trial should be suspended, stopped or continued.

**Update note:** In addition to informing the study's trial management group, a protocol has been developed to appropriately address any concerns regarding the client's safety. The protocol involves informing and seeking supervision from Combat Stress' senior clinical staff and safeguarding leads, liaising with the client's GP, and potential involvement of local crisis teams if necessary. Any identified adverse events or concerns regarding risk will also be brought to the attention of Combat Stress' MDT team for relevant input.

### **Study Suspension or Discontinuation**

The research project would be stopped in the event of several therapy-attributable adverse events. Any serious adverse events will be passed on to trial management group for review, who would have responsibility for assessing whether they are attributable to study participation, setting the threshold for discontinuation and issuing advice to suspend or discontinue. This advice would be acted upon by the researchers, in consultation with the Sponsor.

ESTAIR participants will continue treatment until (1) the clinical aims have been met, where the clinician deems 'reliable recovery' has occurred, or (2) the criteria for withdrawal have been met (4 or more missed sessions).

**Update note:** The criteria for withdrawal has been extended to include if participants do not attend 4 or more sessions in total or two continuous sessions, in the absence of any exceptional circumstances.

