## **Adverse Events**

No severe adverse events have been reported of previously used versions of ESTAIR with people with complex trauma, including in randomised controlled trials (Cloitre et al, 2010). However, we wish to improve the recording and reporting of adverse effects of psychological interventions and have therefore developed a robust protocol for assessing and managing any such risk, which will be completed at end of treatment and at follow-up. The Adverse Events Questionnaire (AEQ; Hutton et al., 2015) was initially developed to investigate adverse effects of a psychosis-specific intervention and was adapted for the present study by removing any psychosis-specific items.

The AEQ used in the present study consists of 25 items (e.g., worsening of mental state, heightened stigma, increased medication use), which are responded to on a 5-point scale ranging from “Not at all” to “Very much”. All participants completing the ESTAIR intervention will complete the trial-completer, patient-rated version of the AEQ. To improve on the reporting of adverse events, participants who withdraw from the study will be asked to complete the early-withdrawal version of the AEQ together with the therapist.

Using an approach applied previously (adapted from Klingberg et al., 2012), we will define serious adverse events as (i) death by suicide; (ii) suicide attempt; (iii) suicidal crisis without attempt; (iv) severe symptom exacerbation (increase of 2 standard deviations or more on the patient or researcher-rated ITQ. Non-severe adverse events will be defined as a score of  $\geq 3$  (agree ‘quite a lot’ or ‘a lot’) on any item on the AEQ (Hutton et al., 2015).

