## **Progression Criteria for a Full Trial**

We will progress for a full trial if we achieve our target recruitment and acquire post-intervention (25 weeks) ITQ data from  $\geq 75\%$  of those randomised.

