## **STATISTICAL CONSIDERATIONS**

### **Sample size**

There are currently no effectiveness studies on the psychological interventions for CPTSD to enable power calculations. Following a pragmatic approach and in line with previous pilot studies in the area of PTSD we will aim to recruit  $n=30$  individuals per arm (total sample = 60). This approach will enable us calculating sample size for an adequately powered trial.

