Phase 2: The primary intention to treat analysis will be conducted to examine differences between the ESTAIR and TAU groups at 25 weeks. This analysis will be conducted using a regression approach, simultaneously regressing the 25 week mean scores of the ITQ, PHQ-9, GAD-7, PHQ-15, and AUDIT onto a dummy-coded binary variable representing the treatment and control group (ESTAIR = 1, TAU = 0). The estimated regression coefficient for each variable indicates the mean difference between the treatment and control group, and the associated  $p$ -values indicate statistical significance. This approach was used as (1) all the model parameters are estimated simultaneously thereby avoiding the need for post-hoc adjustment for multiple testing, (2) the use of robust maximum likelihood (MLR) estimation allows for missing data to be handled efficiently by using all available data (Schafer & Graham, 2002), and third, MLR estimation is robust against deviations from normality and produces unbiased standard errors (West, Finch, & Curran, 1995). Furthermore, the

standardised regression coefficients from this model can be used as a useful analogue to Cohen's *d* as a measure of effect size (Nieminen, Lehtiniemi, Vähäkangas, Huusko, & Rautio, 2013): *d*=0.20 is a 'small' effect, *d*=0.50 is a 'medium' effect, and *d*=0.80 is 'large' effect size.

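### The protocol does not say whether ESTAIR participants who meet the missed-session withdrawal rule are still assessed; if they are not, outcomes are lost in one arm only

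*Combined protocol and SAP*

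**What the plan says.** Under Study Suspension or Discontinuation, ESTAIR participants continue treatment until their clinical aims are met or the criteria for withdrawal are met, at first four or more missed sessions. The update note widens this to those who "do not attend 4 or more sessions in total or two continuous sessions", unless there are exceptional circumstances, which are not defined. TAU has no counterpart.

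Other sections bear on what withdrawal means and what follows from it:

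- Participant Withdrawal or Discontinuation deals with leaving the study and adds: "Non-identifiable data from participants who have been withdrawn will be used to assess the feasibility of the study".
- Adverse Events gives those completing ESTAIR one version of the adverse-event questionnaire, while "participants who withdraw from the study will be asked to complete the early-withdrawal version of the AEQ". It names no group that stops therapy but stays in the trial.
- Procedure has the research assistant contact participants at 25 weeks and again 12 weeks later. It neither excludes nor expressly includes people who met the rule.
- Quantitative analyses, Phase 2: "The primary intention to treat analysis will be conducted to examine differences between the ESTAIR and TAU groups at 25 weeks". The 25-week scores are regressed on a group dummy by robust maximum likelihood, using all available data.
- Progression Criteria: "We will progress for a full trial if we achieve our target recruitment and acquire post-intervention (25 weeks) ITQ data from" at least 75% of those randomised.

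**The concern.** Staff could reasonably follow either of two readings. Under one, meeting the rule ends ESTAIR sessions and the person is still assessed. Under the other, the person has left the study and no 25-week ITQ is sought. The two readings produce different datasets.

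Under the second, the loss is confined to ESTAIR and is tied to engagement, which may well be related to outcome. Someone missing all 25-week measures contributes nothing to the estimated group difference, because the Phase 2 model as written has no baseline score or attendance covariate through which to use what is known about them. Maximum likelihood would then be unbiased only if, within each arm, being missing were unrelated to the 25-week score. No sensitivity analysis is stated.

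Retention is also research question II and half of the progression criterion. A shortfall produced by an administrative reading of the rule would say little about whether a full trial can retain participants.

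**Working it through.** **Inputs from the documents.** Sample size: 30 per arm, 60 in total, chosen pragmatically with no power calculation to reproduce. Progression: at least 75% of those randomised, so 0.75 × 60 = 45. Fifteen missing passes and 16 fails. Sessions: up to 25. The updates to the ESTAIR section give 1 + 5 + 6 + 5 + 7 = 24 once session 25 is merged into the last PTSD session.

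**Assumptions (not in the documents).** Each session is missed independently with probability p of 5%, 10% or 15%; no exemptions are granted; everyone who does not meet the rule, in either arm, gives a 25-week ITQ with probability r of 85% to 100%.

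**Step 1: chance w of meeting the rule.** A participant avoids it with at most three misses, no two adjacent. The number of ways to place k non-adjacent misses in n sessions is C(n−k+1, k), so

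w = 1 − Σ(k=0 to 3) C(n−k+1, k) p^k (1−p)^(n−k).

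For n = 24 and p = 0.10 the terms are 0.0798 + 0.2127 + 0.2492 + 0.1685 = 0.7101, so w = 0.290. At p = 0.05 and 0.15, w = 0.069 and 0.563. With 25 sessions the three values are 0.074, 0.310 and 0.592.

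**Step 2: chance of reaching 45 of 60 if these people are not assessed.** ESTAIR responders are Bin(30, r(1−w)) and TAU responders are Bin(30, r); the chance is P(sum ≥ 45). At p = 0.10 and r = 0.85, ESTAIR response is 0.85 × 0.710 = 0.604 against 0.85 in TAU, and the pooled rate is (0.604 + 0.85)/2 = 0.727.

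| Response among everyone else (r) | p = 10% | p = 15% |
|---|---|---|
| 85% | 40% | 1% |
| 90% | 71% | 3% |
| 95% | 93% | 11% |
| 100% | 99.6% | 30% |

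**Step 3: the same chance if outcomes are still sought** (r = 0.85, p = 0.10). If those meeting the rule respond half as often, ESTAIR response is 0.85 × (1 − 0.290/2) = 0.727 and the chance is 82%. If they respond equally, it is 99%.

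**Step 4: the rule acting alone** (r = 100%). Failure needs 16 of 30 ESTAIR participants (53%) unassessed. Setting w = 16/30 gives p = 14.4% with 24 sessions and 13.9% with 25. At p = 10% the chance of failure is 0.4% with 24 sessions and 0.9% with 25.

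**Step 5: effect on the comparison.** If only those meeting the rule are missing, the ESTAIR available-case mean differs from the mean of all randomised to ESTAIR by w × (mean of the assessed − mean of the unassessed). At p = 10% that is 0.29 of whatever gap exists. The documents give neither its size nor its direction.

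**Step 6: completer definition against the rule.** The ESTAIR section defines a completer as someone with 80% of sessions (0.80 × 25 = 20) and at least one per module. A person whose fourth miss comes late can have attended up to 21 of 25 (84%), or 20 of 24 (83%), and so meet both the completer definition and the withdrawal criterion.

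**The case against.** A reader might infer that the plan removes poor attenders from the study, that intention to treat is therefore broken, and that the rule by itself will defeat the 75% criterion. The documents do not support that.

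- The operative sentence limits treatment, and the phrase for leaving the study that appears in other sections is absent from it.
- The sentence on withdrawn participants' data does not confine those data to feasibility. Its paragraph concerns voluntary, harm-related and adverse-event withdrawal, not missed sessions.
- Procedure contacts participants without exception, the progression denominator is everyone randomised, and Phase 2 declares intention to treat.
- Qualitative outcomes keeps open interviews with four non-completers, so not finishing therapy does not necessarily end research contact.
- The low pass chances mostly combine the rule with ordinary attrition. The 40% includes an assumed 15% loss among everyone else.
- The miss rates are assumed. Clustered misses, rescheduled sessions and the exemption would all change the figures.

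All of this stands, and it makes the point conditional. It does not close the gap: no section says that a person who meets the rule is still assessed, and the section heading, the term used and the two-way split of the adverse-event questionnaire all allow the opposite reading.

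**Conclusion.** The point holds in conditional form. The rule applies to one arm, is named with a term used elsewhere for leaving the study, and carries no statement on later assessment. If those who meet it are not assessed, Phase 2 becomes an available-case comparison with engagement-related loss in ESTAIR only, and 25-week retention falls.

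The size depends on a non-attendance rate that the documents do not give. At 5% the rule touches about 2 of 30 ESTAIR participants (30 × 0.069 = 2.1). At 10% it touches about 9 (30 × 0.290 = 8.7), and passing the retention criterion then depends heavily on background response. At 15% it touches about 17 (30 × 0.563 = 16.9), and passing is unlikely even if everyone else responds. These figures assume 24 sessions, independent misses and no exemptions. The ambiguity should be removed, but it is not evidence that the trial will miss its retention target.

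**What to change.** Leave the attendance rule as it is and add the following to the protocol:

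- Meeting the rule does not end outcome assessment. These participants are contacted at 25 weeks and at the 12-week follow-up unless they refuse further contact.
- They are analysed in their randomised arm and count towards the 75% criterion.
- Outcome data collected before any withdrawal stay in the main analysis.
- Retention is reported by arm as well as pooled.

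Reconcile Participant Withdrawal or Discontinuation with Study Suspension or Discontinuation on what withdrawal means. Reconcile the completer definition in the ESTAIR section with the withdrawal criterion, since one person can now meet both. Which attendance rule is right is for the investigators to settle.

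The cost is protocol and consent wording, and a few extra contacts by the existing research assistant. The gain depends on how many of these participants respond, so the contacts need to be actively pursued.
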